4.2. Survey plan

The patients should have colitis ulcerative in the active moderate or severe phase (only when an existing treatment does not work) and newly receive Humira.

4.3. Target sample size for the survey

1500 patients

<Rationale for the sample size>

1. As this survey is conducted in the clinical settings, we expect that the patients with a treatment history with anti-TNFα drugs may be highly observed. Given that the registration of such patients can increase the dropout rate compared to that of the relevant domestic clinical studies, we calculated that the dropout rate would reach 70% at Week 52. Next, given that the number of patients whose CDAI of the effectiveness endpoint was not

provided in the all-case survey for Crohn's disease accounted for approximately 30%, we need 1500 patients with 30% remission rate, $\pm 5\%$ estimated accuracy of 95% CI and under the conditions where 30% of Mayo score are not assessable (Table 1).

Table 1: The number of patients and accuracy calculated based on the dropout rate

Dropout rate 70%				
C1-	After	Mayo score Number of	At Week 52 Remission rate	
Sample size	Week 52 Sample	patients for	30%	Accuracy
	size	assessment	95%CI	
500	150	105	21.2-38.8	$\pm 8.8\%$
1000	300	210	23.8-36.2	±6.2%
1500	450	315	24.9-35.1	±5.1%
2000	600	420	25.6-34.4	±4.4%

The number of cases with Mayo score provided was calculated as 70% of the total number of patients after Week 52 (i.e., 30% of Mayo score is not provided).

 Next, we examined the accuracy of the remission rate where the number of patients was 1500 as mentioned above with/without treatment experience of anti-TNFα drugs (Table 2).
 We set the following conditions for the accuracy examination:

The all-case survey data in Crohn's-disease patients who used Humira showed that 80% of the patients had been treated with anti-TNF α drugs while 20 % had not. Given that there were many patients who could not benefit from an anti-TNF α agent of prior medication awaiting right after the indication of Crohn's disease was approved, we expect that the same percentage of patients can be enrolled in this survey, too. In this regard, we decided to adopt the similar ratio for the anti-TNF α drug use in this survey and have the patients with and without the treatment history of the drug in an 8:2 ratio.

We set the remission rate of Mayo score at Week 52 in the patients without anti-TNF α drug history as 30% based on the percentage used to estimate the above 1500 patients and in the patients with the history as 10% based on the data in an overseas clinical study (M06-827 Study).

Table 2: The Accuracy of remission rate with/without treatment history of anti-TNFα drugs

y			J	0
	Mayo score Number of patients for assessment	At Week 52 Remission rate	95%CI	Accuracy
With a treatment history of anti-TNFα drugs	252	10%	6.1-13.9	±3.8%
Without a treatment history of anti-TNFα drugs	63	30%	17.9-42.1	±12.1%

These results suggest that the value might be less accurate due to a fewer number of patients in the group of no treatment history of anti-TNF α drugs while the value in the group with the treatment history will be accurate enough for the examination. (Table 2)

3. For the safety, tuberculosis occurred in a patient (1/177 patients, 0.6%) as an important adverse event (the causal relationship with Humira: probably not related) in a relevant domestic clinical study. If data from 1500 patients are collected based on the incidence, we can assess the accuracy with the 95%CI for the incidence of 0.3%-1.1%. Even if the incidence of tuberculosis reached 2% in this survey, which is higher than that of the clinical study, the confidence interval would range between the minimum 1.35 and the maximum 2.84 by collecting 1500 patients. In this case, the incidence of tuberculosis (as an adverse event) observed in a clinical study for arthritis rheumatoid exceeds 1.0%, meaning that the accuracy is assessable.

Therefore, we have 1500 patients as the target sample size.

5. Items to be analyzed and the methods

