2. Next, for the presence or absence of history of use of anti-TNFα products, the accuracy of the remission rate used for setting the above sample size of 1500 patients was evaluated (Table 2). The following conditions were specified for the evaluation:

In data from the all-case survey of Humira in patients with Crohn's disease, 80% and 20% of the patients had used and had not used anti-TNF α products. Immediately after the drug was approved for Crohn's disease, because there were many patients waiting for the drug such as non-responders to anti-TNF α products in previous treatment, patients are likely to be enrolled in the present survey at the same ratio. Therefore, the rate for the use of anti-TNF α products in the survey was selected to be 80% and 20% for patients have used and have not used them.

The remission rate based on the Mayo score at Week 52 was set to 10% for patients who have used anti-TNF α products based on data from an overseas clinical study (M06-827) and 30% for patients who have not used them which was utilized for calculating the above sample size of 1500 patients.

Table2 Remission rate of history of anti-TNFα products use

	No. of patients	Remission		
	assessed for	rate at	95%CI	Accuracy
	Mayo score	Week 52		
History of anti-TNFα products	252	10%	6.1~13.9	±3.8%
use	232	10%	0.17~13.9	±3.8%
Without history of use of anti-	62	200/	17.9~42.1	±12.1%
TNFα products	63	30%	17.9° ~42.1	±12.1%

Based on these results, while the accuracy is poor because the number of patients in the group without history of use of anti-TNF α products is small, the data from the group with a history of use of anti-TNF α products is assumed to be an assessable numerical value (Table 2).

In a domestic clinical study of this drug in patients with ulcerative colitis (Study M10-447: 52 weeks), adverse events occurred in one patient where the incidence rate was 0.6% (1/177). On the basis of this incidence, when 1500 patients are accumulated, the 95% confidence interval for the incidence would be 0.3 to 1.1% and assessable. Even if the incidence of tuberculosis is 2%, which is higher than that in the clinical study, in this survey, by accumulating 1500 patients, the upper and lower limit of the confidence interval would be 2.84 and 1.35, respectively. Hence, because the incidence of tuberculosis (as an adverse event) shown in the Japanese clinical study in patients with rheumatoid arthritis is higher than 1.0%, it is evaluable.

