	[6] recovering [7] recovered
Death case	At least a piece of data on "death" is found as the outcome of the adverse
Death case	events during the safety analysis period.
	Use the onset date for company assessment provided in "AE matching
	results".
	When the first administration date of Humira and the adverse-event onset
	date can be identified as the complete date, they can be used for
Days from the first	calculation.
administration date of	When the first administration date of Humira <= the adverse-event onset
Humira to the	date
adverse-event onset	Adverse-event onset date - the first administration date of Humira + 1
date	When the first administration date of Humira > the adverse-event onset
	date
	Adverse-event onset date - the first administration date of Humira
	When more than one identical PT is found in a patient, use the first onset
	date to identify the adverse event to be counted.
Days from the	Use the onset date and the outcome confirmation date (recovered or
adverse-event onset	recovering)for company assessment provided in "AE matching results".
date to the outcome	When the adverse-event onset date and the outcome confirmation date can
confirmation date	be identified as the complete date, they can be used for calculation.
(recovered or	Outcome confirmation date - adverse-event onset date + 1

Data name	Derivation and calculation methods
recovering)	When more than one identical PT is found in a patient, choose the event which persisted longest until the recovery or the outcome confirmation date.
Incidence of adverse reactions, incidence of serious adverse reactions, incidence of adverse events, incidence of serious adverse events	Calculate the incidence of adverse reactions, incidence of serious adverse reactions, incidence of adverse events, incidence of serious adverse events with the number of patients with any of the reactions/events in numerator and the number of patients in the safety analysis group in denominator. Provide how to calculate in each table at Chapter 13 and thereafter if other calculation methods are used.

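### The tuberculosis intervals are correct for a crude proportion in 1500 patients, but they are not the precision for a 52-week risk under the plan's own 70% dropout

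*SAP*

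**What the plan says.** Item 1 of the sample-size rationale (SAP 4.3; protocol section 2) allows for heavy loss: "we calculated that the dropout rate would reach 70% at Week 52". Table 1 accordingly cuts 1500 to 450 at Week 52, and then to 315 with a Mayo score.

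The safety rationale (SAP 4.3 item 3) makes no such allowance. Its starting point is that "tuberculosis occurred in a patient (1/177 patients, 0.6%) as an important adverse event". The protocol gives the source of the 1/177: "In a domestic clinical study of this drug in patients with ulcerative colitis (Study M10-447: 52 weeks". The SAP concludes that "we can assess the accuracy with the 95%CI for the incidence of 0.3%-1.1" per cent, and the protocol that "when 1500 patients are accumulated, the 95% confidence interval for the incidence would be 0.3 to 1.1% and assessable". A second scenario follows: "Even if the incidence of tuberculosis reached 2% in this survey", "the confidence interval would range between the minimum 1.35 and the maximum 2.84 by collecting 1500 patients". Both documents then refer to a tuberculosis incidence above 1.0% in a rheumatoid arthritis study.

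Three further provisions matter:
- SAP section 2 counts events in a discontinued patient only up to 28 days after the final administration. For other patients the window runs to Week 56.
- SAP 10.2 defines incidence as patients with the event, with "the number of patients in the safety analysis group in denominator".
- No rate per unit of exposure is planned in any table.

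**The concern.** A proportion from a 52-week study is carried over to 1500 patients, most of whom are assumed to leave before Week 52 and whose events stop counting shortly after the last dose. With less time at risk, fewer cases are expected than 0.6% or 2% of 1500. The crude percentage then understates a 52-week risk.

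This matters because protocol section 2 says that 1500 was chosen so that the survey can verify the clinical study's safety and effectiveness results, and the rationale cites incidences from two other studies. Tuberculosis is a priority item and the only safety event used to support the sample size. A crude percentage from shortened follow-up, set beside 52-week results, could look reassuringly low.

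**Working it through.** **1. Reproduce the stated intervals.** The exact binomial (Clopper-Pearson) method, which the SAP names for its remission rates, gives:
- 0.6% × 1500 = 9 cases; 9/1500 gives 0.27 to 1.14%, which rounds to 0.3 to 1.1%.
- 2% × 1500 = 30 cases; 30/1500 gives 1.35 to 2.84%.

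Both match, so there is no arithmetic error.

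**2. Exposure under 70% dropout.** From the documents: 1500 patients, 30% remaining at Week 52, and a window that closes 28 days after the last dose (Week 56 for completers). Assumed here, because the documents do not give it: the dropout pattern. A year is taken as 52 weeks.
- Exponential dropout: hazard = −ln(0.30) = 1.204; mean exposure = 0.70/1.204 = 0.581 years (30.2 weeks); × 1500 = 872 patient-years.
- Linear dropout: mean exposure = 1 − 0.70/2 = 0.65 years (33.8 weeks); × 1500 = 975 patient-years.
- The 28-day tail adds 1500 × 28/364 = 115 patient-years, which is 13% of 872 or 12% of 975. The totals become 987 and 1090.

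**3. Expected cases and intervals.** Assume a constant tuberculosis hazard, with the 52-week risk as the yearly rate: expected cases = risk × patient-years, rounded to whole cases. Crude intervals are exact binomial on 1500. Rate intervals are exact Poisson.

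| Dropout pattern | Patient-years | 52-week risk | Expected cases | Crude % (95% CI) | Per 100 patient-years (95% CI) |
|---|---|---|---|---|---|
| Exponential, no tail | 872 | 0.6% | 5.2 → 5 | 0.33 (0.11–0.78) | 0.57 (0.19–1.34) |
| Exponential + 28 days | 987 | 0.6% | 5.9 → 6 | 0.40 (0.15–0.87) | 0.61 (0.22–1.32) |
| Linear, no tail | 975 | 0.6% | 5.9 → 6 | 0.40 (0.15–0.87) | 0.62 (0.23–1.34) |
| Linear + 28 days | 1090 | 0.6% | 6.5 → 7 | 0.47 (0.19–0.96) | 0.64 (0.26–1.32) |
| Exponential, no tail | 872 | 2% | 17.4 → 17 | 1.13 (0.66–1.81) | 1.95 (1.14–3.12) |
| Exponential + 28 days | 987 | 2% | 19.7 → 20 | 1.33 (0.82–2.05) | 2.03 (1.24–3.13) |
| Linear, no tail | 975 | 2% | 19.5 → 20 | 1.33 (0.82–2.05) | 2.05 (1.25–3.17) |
| Linear + 28 days | 1090 | 2% | 21.8 → 22 | 1.47 (0.92–2.21) | 2.02 (1.26–3.05) |

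Against 9 and 30, expected cases fall by 27% (1 − 1090/1500) to 42% (1 − 872/1500).

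**4. Sensitivity to the assumptions.**
- Very late dropout: if all 70% left at Week 44, exposure including the tail would be 1500 × (0.30 + 0.70 × 44/52 + 28/364) = 1454 patient-years. At 2% that is 29 cases, crude interval 1.30 to 2.76%, close to the plan's figure.
- Early onset: if the tuberculosis hazard halves every 13 weeks (illustrative), with linear dropout and the tail, the expected crude proportion is (0.02/0.9375) × [0.30 × (1 − 2^(−56/13)) + 0.70 × (1 − 0.338 × 2^(−4/13))] = 1.69%. Here 0.9375 = 1 − 2^(−4), and 0.338 is the mean of 2^(−t/13) over Weeks 0 to 52. That is about 25 cases, crude interval 1.08 to 2.45%.

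**The case against.** The strongest reply is that 1500 is the right denominator for the planned estimator. Early discontinuation is not among the listed exclusions from the safety analysis group, and a case report form is completed at discontinuation, so dropouts stay in. Dropout shrinks the number with a Week 52 Mayo score, but not the number in a crude incidence; treating the two differently is not in itself a contradiction. The 2% scenario is also worded as an incidence seen in this survey, and 30/1500 gives 1.35 to 2.84% whatever the follow-up. All of this stands. Nor do the documents say that the 1500 are fully followed for 52 weeks.

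A reader might go further and infer that the stated intervals are wrong, that the safety sample is really 450, or that a 2% risk could not be told apart from 1.0%. The documents support none of these:
- The intervals reproduce exactly.
- Using 450 would discard the exposure and events of the dropouts.
- No test against 1.0% is stated. Whether the crude interval excludes 1.0% depends on dropout timing and onset pattern, as the sensitivity cases show.

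It can also be said that the 0.6% is itself very uncertain, since 1/177 has an exact 95% interval of 0.01 to 3.1%, and that 1500 was set by remission precision. Both are true, so nothing here argues for a different sample size. Neither is a reason to leave the survey's own assumed dropout out of its safety rationale.

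Tables 2.6 and 2.7 do use patients still under observation in each period. They cover adverse reactions only, whereas the tuberculosis comparison is made on adverse events, and they give no person-time rate.

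**Conclusion.** This is a worthwhile, inexpensive improvement and not a correction of an error. The intervals hold for observed crude proportions of 0.6% and 2% in 1500 safety patients, an upper bound because unlocked forms and exclusions will reduce that number. They do not describe the precision for a 52-week tuberculosis risk under 70% dropout.

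With a constant hazard and exponential or linear dropout, with or without the 28-day tail, a 52-week risk of 0.6% gives about 5 to 7 cases, with crude intervals from 0.11–0.78% to 0.19–0.96%. A risk of 2% gives about 17 to 22 cases, with crude intervals from 0.66–1.81% to 0.92–2.21%. Late dropout or front-loaded onset would narrow the difference.

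The comparators need equal care. Dropout in the 177-patient study and follow-up behind the 1.0% are not given, so neither can be read as a clean 52-week risk, and a person-time rate cannot be set directly against the 1.0%.

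**What to change.** - In protocol section 2 and SAP 4.3 item 3, state that 0.3–1.1% and 1.35–2.84% apply to the crude proportion in the safety analysis group. Add the expected range of cases and intervals under 70% dropout, with the assumed dropout pattern and hazard.
- In Tables 2.4.1 to 2.4.4, add beside the crude percentage the incidence rate per 100 patient-years, with time counted from first dose to first event or end of the safety window, and an exact Poisson 95% interval.
- Add a note that the follow-up behind the 1/177 and 1.0% comparators is not fully given, so comparisons with them are indicative.

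The cost is a few restated figures, one extra column and slightly less favourable stated precision. First and final administration dates are already derived in SAP 10.1 and the safety window is defined in section 2, so no new data are needed and the sample size does not change.

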5.1. Analysis items

- 1) Items regarding patient composition
 - [1] Sample size for registration
 - [2] The number of patients whose survey form was locked
 - [3] The number of patients in the safety analysis group
 - [4] The number of patients in the effectiveness analysis group
- 2) Items regarding safety
 - [1] A list of the onset status of adverse reactions/infections
 - [2] Factors which may affect the safety
 - Incidence of adverse reactions per patient background, etc.
 - Presence/absence of the experience with biological products, and the relation with it
 - Safety for long-term use
 - Safety relationship when anti-adalimumab antibody was measured
 - Presence/absence of self-administration and the relation with it
 - [3] Adverse events which occurred during or after the administration
 - A list of the onset status of serious adverse events, etc.
 - The onset status of intestinal infection of cytomegalovirus colitis
 - [4] Warnings, Careful Administration section, and major adverse events subject to

special attention in Important Precautions section in Humira's package insert (infections including tuberculosis, malignant tumour, injection site reactions, allergic reaction, demyelinating disorders, lupus-like syndrome and blood disorder)

- [5] The administration-error status at self-administration
- [6] The safety in pediatric patients with colitis ulcerative

3) Items regarding effectiveness

- Changes in the effectiveness until Week 52 of administration (Mayo score, partial Mayo score, etc.)
- Presence/absence of the experience with biological products, and the relation with it
- Effectiveness per prior medication history
- Effectiveness for long-term use (including the percentage of the secondary failure)
- Effectiveness relationship when anti-adalimumab antibody was measured
- Effectiveness in pediatric patients with colitis ulcerative

4) Items regarding patients with special backgrounds

A list of onset status of adverse reactions/infections in patients with special backgrounds such as pediatrics, the elderly, pregnant woman, renal impairment, hepatic function disorder, etc.

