Name of center, enrollment date, name of department, name of physician in charge, identification No. of patient, patient's consent, birth date or age, sex, pregnant or lactating status(in case of women), race, reason for use, initial (or scheduled) day of administration, administration status, examination category, contraindication items, careful administration, presence or absence of prior medications for ulcerative colitis and their effects, use history of biological products, tuberculosis and infection tests (tuberculin skin test, Quanti-Feron®

test, chest X-ray test, and CT test), HB virus tests (HBs antigen, HBs antibody, and HBc antibody), preventive administration of anti-tuberculosis agents, and clinical laboratory test values (β-D-glucan, peripheral WBC count, and peripheral lymphocyte count) before administration should be recorded.

(3) CRF

1) Patient information

height, body weight, smoking history, pathological condition of ulcerative colitis, disease duration, complication, past history, and allergy history

- 2) Ulcerative colitis-affected site
- Treatment history of ulcerative colitis with anti-TNFα
 Presence or absence of prior treatment with anti-TNFα, administration history, and reason for discontinuation
- 4) Prior medications or therapy for ulcerative colitis (within 3 months before administration of this drug)

History and type of prior medications or therapy

5) Administration status of this drug

Initial administration: Category of administration method, initial dose, and first

administration day

2nd administration: Category of administration method, 2nd dose, and day of 2nd

administration

3rd and subsequent administrations: Category of administration method, daily dose,

administration frequency, administration period, and reasons for

change to the dose and administration frequency

Self-injection: Presence or absence of consent to initiation of self-injection and

record on initiation of self-injection

Malpractice of self-injection: Y/N, onset day, and type/reason

6) Discontinuation of survey

Reason for discontinuation

7) Administration status of anti-tuberculosis agents

Presence or absence of administration of anti-tuberculosis agents, product name, daily dose, and administration period

8) Administration status of concomitant drug(s)

Concomitant drug for ulcerative colitis: drug name, reason for use, administration route, dose, and administration period

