- 9) Other concomitant drugs: drug name, reason for use, administration route, dose, and administration period
- 10) Drugs/combination therapies other than medication for ulcerative colitis

Presence or absence of drugs/combination therapies other than medication for ulcerative colitis, name of therapy, and therapeutic duration

11) Presence or absence of onset of tuberculosis or serious respiratory disorders

Examination day, imaging diagnostic method, abnormal findings, and abnormality

12) Mayo Score

Examination day (at initiation of administration, week 4, 8, 16, 24, 32, and 52 of administration, and discontinuation of administration)

13) CRP

Examination day (at initiation of administration, week 4, 8, 16, 24, 32, and 52 of administration, and discontinuation of administration)

14) Endoscopic finding

Examination day (at initiation of administration, week 24, 52 of administration, and discontinuation of administration)

15) Overall improvement (judgment by attending physician)

Judgment day (at week 52 of administration or at discontinuation)

Overall improvement (Remarkably effective, Effective, Ineffective, and Unevaluable)

16) Adverse events (including abnormal change in laboratory values)

Occurrence of adverse events, name of adverse events, onset day, seriousness, causal relationship to this drug, suspected drug(s), symptom and clinical course, treatment (with this drug or symptomatic treatment), outcome, laboratory values (if abnormally changed), and judgment reason if no causality

17) Key survey items

Infection, tuberculosis, malignant tumor, administration site reaction, autoimmune disease, pancytopenia, demyelinating disorders, congestive cardiac failure, and interstitial pneumonia

18) Measurement of anti-adalimumab antibody

If measurement of anti-adalimumab antibody is judged to be necessary

9. Analysis and Methods

- (1) Analytical items
 - 1) Patient population
 - 1. No. of enrolled patients
 - 2. No. of CRFs recovered
 - 3. Safety evaluation set
 - 4. Efficacy evaluation set
 - 2) Safety
 - 1. List of adverse reactions and infections
 - 2. Factors likely to affect the safety

- Incidence of adverse reactions by patient background
- Presence or absence of the use experience with anti-TNFα preparation and the relationship of safety.
- Safety in Long-Term administration
- Relationship of safety when anti-adalimumab antibody was determined
- Safety in patients conducting self-administration

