- 3. Adverse events which developed during or after administration
 - List of serious adverse events
 - Status of onset of intestinal infections including cytomegalovirus colitis, etc.
- 4. Main adverse events (infections including tuberculosis, malignant tumor, injection site reaction, allergic reaction, demyelinating disease, lupus-like syndrome, blood disorder) for which attention is called in the sections of warning, careful administration and important basic precautions in the package insert of the study drug
- 5. Onset of self-injection malpractice
- 6. Safety in pediatric UC patients

3) Efficacy

- Change in efficacy (Mayo score, Partial Mayo score etc.) by Week 52 of administration
- Presence or absence of the use experience with anti-TNF α preparation and the relationship of efficacy.
- Efficacy by the history of previous treatment
- Efficacy (including the incidence of secondary ineffectiveness) in long-term administration
 - Relationship between efficacy and safety when anti-adalimumab antibody was determined
 - Efficacy in pediatric UC patients
- 4) Patients with special background

List of adverse reactions and infections in patients with special background such as children, elderly, pregnancy, renal dysfunction, and hepatic dysfunction

(2) Analytical methods

Appropriate methods such as χ^2 test will be used, depending on the scale and property of the analytical data.

10. Action to be taken when use in pregnant woman was found

The effects on parturition and newborn are followed up as much as possible, if use in pregnant women was found.

11. Organization of Surveillance

This follows the master plan for post-marketing surveillance. The trustee appears in "12. Name

and Address of Person Who Was Entrusted with This Duty and Scope of the Duty" below.

12. Name and Address of Person Who Was Entrusted with This Duty and Scope of the Duty

(1) Trustee 1

2) Scope of duty

Implementation of "Specified Long-Term Use-Results Surveillance" (Asking the center or department for implementation of surveillance, contract, recovery of enrollment form and reinvestigation, recovery of CRF and reinvestigation, progress report of duty, and collection of information on adverse events (including abnormal change in laboratory values))

(2) Trustee 2

2) Scope of duty

The implementation of special use-results survey (patient enrollment activities, reporting the progress of activities, data management activities, statistical analysis activities, etc.)

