Presence/absence of prior medication (tacrolimus & ciclosporin)	Refer to "171218 drug list_UC". If prior-medication data of the applicable drug code are provided in the survey form, or if tacrolimus & ciclosporin in the survey form is checked, regard the case as "with tacrolimus & ciclosporin". Others are "without tacrolimus & ciclosporin".
Presence/absence of	Refer to "171218 drug list_UC". If prior-medication data of the

Data name	Derivation and calculation methods
prior medication	applicable drug code are provided in the survey form, or if antibiotics
(antibiotics)	in the survey form is checked, regard the case as "with antibiotics".
	Others are "without antibiotics".
	When any items other than biological products in the survey form are
	checked, and when prior medication data on the drug code applicable
Presence/absence of	to the drug other than aminosalicylic acid drug, corticosteroids,
prior medication (others)	azathioprine, 6-mercaptopurine, tacrolimus, ciclosporin and
	antibiotics are included in reference to "171218 drug list_UC",
	regard it as "with others". Other cases are "without others".
Presence/absence of	Refer to "171218 drug list_UC". If prior-medication data of the
	applicable drug code are provided in the survey form, or if Infliximab
prior medication (Infliximab)	in the survey form is checked, regard the case as "with Infliximab".
(IIIIIXIIIIau)	Others are "without Infliximab".
	When 'biological products' is checked in the survey form, and when
Presence/absence of	prior-medication data of the drug codes other than Infliximab are
prior medication (other	provided in the survey form in reference to "171218 drug list_UC",
biological products)	regard the case as "with other biological products". Others are
	"without other biological products".
	The cases with either "with prior medication (Infliximab)" or "with
	prior medication (other biological products)" are regarded as "with a
Presence/absence of	treatment history with biological products". Others are "without a
treatment history with	treatment history with biological products".
biological products	As for presence/absence of the history by 'detailed classification
biological products	"with" biological products', if the applicable data among
	"Infliximab" and "other biological products" are contained, the case
	is regarded as "with" the history. Others are "without" the history.
	When the description is made in "Prior treatment for colitis ulcerative

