discontinuation, other	the condition improved, the condition worsened
reasons	Poor adherence, for study
Sex	Man, women, unknown/not provided
Pregnancy/nursing	Not pregnant/nursing, pregnant, nursing, unknown/not provided
Race	Japanese, other Asians, others, unknown/not provided
Age (in years)	$<15, \ge 15$ and $<65, \ge 65$, unknown/not provided
	<30, ≥30 and <40, ≥40 and <50, ≥50 and <60, ≥60, unknown/not
Body weight (kg)	provided
BMI(kg/m ²)	$<18.5, \ge 18.5 \text{ and } <25, \ge 25 \text{ and } <30, \ge 30, \text{ unknown}$
Duration of illness (in	
years)	$<2, \ge 2$ and $<10, \ge 10$, unknown/not provided
Indication (registration	Colitis ulcerative, others, not provided
form)	

Data	How to stratify
Allergy history	Without the history, with the history, unknown/not provided
Smoking history	Without the history, with the history, unknown/not provided
Detailed classification of smoking history	Smoking, only in the past (not smoking now), unknown
Tuberculosis test	Not conducted, conducted
Hepatitis B test	Not conducted, conducted
Complications	Without the history, with the history, unknown/not provided
Detailed classification of complications	Liver disorder, renal disorder, blood disorder, respiratory disorder, others
Other classification of complications	Diabetes mellitus, osteoporosis, malignant tumour, others
Medical history	Without the history, with the history, unknown/not provided
Detailed classification of medical history	Tuberculosis, non-tuberculous mycobacteriosis, interstitial pneumonia, bronchitis bacterial, aplastic anaemia, pancytopenia, malignant tumour, others
Prior medications for colitis ulcerative	Without the history, with the history, unknown/not provided
Details classification of	Infliximab, other biological products, aminosalicylic acid products,
prior medications for	corticosteroid, azathioprine & 6-mercaptopurine, tacrolimus &
colitis ulcerative	ciclosporin, antibiotics, prior medication: others
Prior treatment for colitis ulcerative	Without the history, with the history, unknown/not provided
Details classification of prior treatment for colitis ulcerative	Leukocytapheresis, surgery, enteral nutrition therapy, intravenous nutrition therapy, others
Treatment history with biological products	Without the history, with the history, unknown/not provided

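### The protocol's anti-TNFα-experience subgroup is replaced in the SAP by history of any biological product, without a stated reason, and no SAP variable is guaranteed to equal it

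*SAP*

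**What the plan says.** **Protocol.** Section 9(1) lists, under safety, "Presence or absence of the use experience with anti-TNFα preparation and the relationship of safety". The efficacy list has a parallel item, which ends "preparation and the relationship of efficacy". Section 8(3), CRF item 3, collects the exposure directly: "Presence or absence of prior treatment with anti-TNFα, administration history, and reason for discontinuation". Separately, the enrollment form in section 8(2) records "use history of biological products". The amendment log in section 14 shows one change, to adverse event reporting, so the anti-TNFα wording is current.

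**SAP.** Section 5.1 follows the protocol's list closely, but for both safety and effectiveness this item becomes "Presence/absence of the experience with biological products, and the relation with it". Section 10.1 supplies the derivation. It begins "The cases with either 'with prior medication (Infliximab)' or 'with" and continues "prior medication (other biological products)' are regarded as 'with a" positive history; everyone else is without. Section 11 stratifies by "Treatment history with biological products". Tables 2.18 and 2.18.1 split by that variable. Tables 2.9 and 3.4, and 3.4.1 by reference to 3.4, test three factors: biological product, infliximab, and other biological product.

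SAP 4.3 and its Table 2 still set out the precision argument by anti-TNFα history, in an 8:2 ratio. The revision history in SAP section 1 gives no reason for the change of term.

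**The concern.** Factors affecting safety and effectiveness are a stated objective in both documents, and anti-TNFα experience is one the protocol names under each. A reader who goes to the SAP tables for that comparison finds a variable with a different definition and no statement that the two coincide.

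Any biologic is at least as wide a category as anti-TNFα. If it is strictly wider, some patients without anti-TNFα exposure sit in the exposed group, and the tables do not answer the protocol's question. The precision quoted in SAP Table 2 would then also not strictly describe the groups analysed.

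**Working it through.** **1. The plan's own subgroup figures.** Inputs from SAP 4.3: 1500 patients, 70% dropout at Week 52, 30% of Mayo scores not assessable, 80:20 split by anti-TNFα history, remission 10% with and 30% without.

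- Evaluable: 1500 × 0.30 × 0.70 = 315. Split: 315 × 0.80 = 252 and 315 × 0.20 = 63.
- Interval, normal approximation with continuity correction: p ± [1.96·√(p(1−p)/n) + 1/(2n)].
- With history: 1.96·√(0.10·0.90/252) + 1/504 = 0.0390, giving 6.1 to 13.9%.
- Without history: 1.96·√(0.30·0.70/63) + 1/126 = 0.1211, giving 17.9 to 42.1%.

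Both intervals in Table 2 reproduce. The printed ±3.8% for the first group is 0.1 below what its own interval implies; this has no bearing here. So the SAP's precision statement is built on anti-TNFα history.

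**2. How each kind of patient is classified.**

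| Prior biologic use | Protocol: anti-TNFα | SAP: any biologic | SAP: infliximab | SAP: other biologic |
|---|---|---|---|---|
| Infliximab only | with | with | with | without |
| Another anti-TNF agent only | with | with | without | with |
| Only a biologic that is not anti-TNF (if the list has one) | without | with | without | with |
| None | without | without | without | without |

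The pooled variable can differ from the protocol's subgroup only in the third row. The infliximab factor avoids that but misplaces the second row. The other-biologic factor does not separate the second row from the third. Whether the third row is empty depends on the file 171218 drug list_UC, which is not in the documents. SAP 10.1 does not limit other biological products to anti-TNF agents, and it does not name the anti-TNFα CRF item as a source.

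**3. Whether a direction of effect follows.** The documents give no count for the third row, so this is an assumption, used only to test the sign. Let a share s of the 63 evaluable naive patients fall there.

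- s = 0: groups stay 252 and 63.
- s = 10%: 6.3 move, giving about 258 and 57.
- s = 20%: 12.6 move, giving about 265 and 50.

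At s = 20%, with 30% remission in the naive group as a whole:

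- Moved patients remit at 30%: with = (25.2 + 3.78)/264.6 = 10.95%, without = 30%, difference 19.05 points.
- Moved patients remit at 10%: with = (25.2 + 1.26)/264.6 = 10.0%, without = (18.9 − 1.26)/50.4 = 35.0%, difference 25.0 points.

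Against the planned 20 points, the contrast can narrow or widen.

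**4. What this does not size.** The 10% and 30% are full-Mayo remission at Week 52. Tables 2.9, 2.18 and 2.18.1 report adverse reactions, 3.4 uses general improvement, and 3.4.1 uses partial Mayo remission at final assessment. The only full-Mayo remission table, 3.1.2, is not split by treatment history. Step 3 therefore describes no planned output.

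**The case against.** The strongest reply is that this is only a difference of vocabulary. Among the protocol's CRF items on previous treatment, the anti-TNFα item alone records why the treatment was stopped; the item for other prior medication records only history and type. SAP section 11 breaks positive biologic history down into infliximab, other biological products and reasons for discontinuation, which matches the anti-TNFα item. The documents name no biologic outside the anti-TNF class. If the drug list holds none, the two definitions coincide.

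Much of this stands. A shared source is plausible, and infliximab does have its own row in Tables 2.9, 3.4 and 3.4.1. But plausibility is not a definition. The protocol uses both terms, on different forms, and the SAP nowhere says they mean the same agents. The infliximab row does not reach other anti-TNF agents, and Tables 2.18 and 2.18.1 have no such row.

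A reader might go further and infer that naive patients are in fact moved into the exposed group, that the expected 10% against 30% contrast is diluted, or that a known amount of precision is lost. The documents support none of these. The drug list is unseen, the direction depends on how any moved patients respond, and the 10% and 30% belong to an endpoint that no planned table splits by history.

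**Conclusion.** The point holds as an undocumented change of definition, not as a demonstrated bias. The protocol names anti-TNFα experience for both safety and efficacy; the SAP delivers history of any biologic, while its own sample-size rationale keeps the anti-TNFα definition.

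The size is unknown. It is zero if the drug list contains only anti-TNF agents. Otherwise it equals the number of anti-TNFα-naive patients who used some other listed biologic, all of whom would be classed as having a history. No direction of effect on any contrast can be stated. The change should be made because it costs little and restores a subgroup the protocol names.

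**What to change.** In SAP 10.1, define a yes/no variable for anti-TNFα history from CRF item 3 together with the drug codes for anti-TNF agents (infliximab and any others on the list), and name those agents. Add it to section 11 and restore the protocol's term in section 5.1. Use it for the protocol's subgroup in Tables 2.18, 2.18.1, 2.9, 3.4 and 3.4.1, and keep any-biologic history as a supplementary row. If the two definitions prove to coincide, the listed agents will show it and the results will not change.

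The cost is one derived variable from data the protocol already collects, plus the SAP wording and the reprogramming of five tables.
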